**c. PRE-OPERATIVE**

Once revision candidates have been identified and consented, patients will be randomized to traditional vs. barbed suture closure via RedCap. Medical records will be reviewed for baseline patient characteristics, preoperative patient data and laboratory values (Table 1). Prior to operation, a clinical image of the patients existing scar will be obtained for research purposes.

**Table 1.** Collected Baseline Patient Characteristics

Baseline Patient Characteristics
Age
Gender
Body mass index (BMI)
Zip code
American Society of Anesthesiologist (ASA) Score
Insurance type
Preoperative complete blood count (CBC), basic metabolic panel (BMP), and hemoglobin A1c (HbA1c)
Presence of diabetes mellitus
Cigarette smoking status
E-Cigarette smoking status
Immunocompromised status
Charlson Comorbidity Index (CCI)
Indication for Revision Arthroplasty

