#### Group #1:

Traditional closure will consist of arthrotomy (deep layer) closed with figure of eight number 1 vicryl plus followed by closure of the intermediate layer with 0 Vicryl plus. The intermediate layer will be performed at surgeon's discretion especially in thin patients. Subdermal layer with 2-0 vicryl suture followed by subcuticular 3-0 monofilament suture (monocryl PLUS, Ethicon; Johnson & Johnson) and Dermabond advanced. This is considered routine care at NYU Langone Orthopedic Hospital. There is no established protocol for suturing the wound.

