### 3.2.2.RANDOMIZATION

Once Revision TJA candidates are successfully screened, patients meeting eligibility criteria will be randomized into either the barbed or conventional closure group. After informed consent is obtained and the screening interview is conducted, the principle investigator/sub- investigator or research assistant will electronically randomize a patient to a study group (barbed or conventional closure group) using the REDCap database (web-based secure database application).The NYU Statistics Department will provide the randomization scheme that will be used within the REDCap database to randomly assign patients to one of the two treatment groups. Each patient who qualifies for entry into the study will be assigned a unique study number in chronological order.

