#### **4.2 EXCLUSION CRITERIA**

1. Patient is  $\leq$  18 years of age
2. Patient is unable to provide written consent
3. Patient has active infections in the operative leg/joint
4. Known Allergy to Suture material
5. Underlying Dermatological diseases affecting surgical site including dermatitis, eczema, or psoriasis; connective tissue or vascular disorders or diseases that would adversely affect wound healing; metastatic cancer; renal insufficiency (dialysis); steroid dependence; malnourishment; and other disease processes resulting in an immunocompromised state. Diabetes, smoking and obesity will be allowed as they are frequent comorbidities in our revision joint population
6. Anterior total hip replacement
7. Stage 1 of two stage revision for infection
8. Closure performed by plastic surgeon, including flap coverage

Vulnerable populations will not be enrolled in this study.

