#### **5.1 Withdrawal Criteria**

1. Failure to attend regularly scheduled follow up appointments
2. Deviation from closure protocol

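### The arm is allocated before surgery and not withheld until closure, so a patient who becomes ineligible in theatre can drop out through a decision made with the allocation known

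*Combined protocol and SAP*

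**What the plan says.** Two sections of the combined protocol and SAP fix when the arm is drawn. Section 9.c, headed as pre-operative, states "Once revision candidates have been identified and consented, patients will be randomized to traditional vs. barbed suture closure via RedCap". Section 3.2.2 places the step "After informed consent is obtained and the screening interview is conducted" and adds that the principal "investigator/sub- investigator or research assistant will electronically randomize a patient to a study group (barbed or conventional closure group) using the REDCap database". Neither section ties the draw to the start of closure or keeps the result from the operating surgeon, and no other section describes masking.

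Three exclusions in section 4.2 bear on events in theatre:

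- Exclusion 8: "Closure performed by plastic surgeon, including flap coverage". This describes how the operation ends.
- Exclusion 7: "Stage 1 of two stage revision for infection".
- Exclusion 3: "Patient has active infections in the operative leg/joint".

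Section 5.1 separately lists "Deviation from closure protocol" as a ground for withdrawal. No section says how a randomised patient found ineligible during the operation is handled, and section 12 names no analysis population.

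**The concern.** The two techniques differ only from the moment closure begins (section 3.2.1), and the primary endpoint is the time closure takes (section 2.3). Everything between allocation and that moment is exposed to knowledge of the arm without any benefit to the trial.

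The patient most at risk is one whose wound is handed to a plastic surgeon in theatre. That patient was eligible at randomisation and becomes ineligible afterwards, possibly by the decision of someone who knows which closure was assigned. Section 1.1 says that closure at this institution follows surgeon preference, and section 3.2.1 puts usual practice at about 75% conventional and 25% barbed, so surgeons do not come to the allocation without a prior preference.

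Such wounds may well be among the slower ones to close. If they leave one arm more often than the other, the comparison of closure times is no longer between randomised groups. An intention-to-treat rule would keep a deviating study closure in the analysis, but it cannot supply a closure time where no study closure took place.

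**Working it through.** **Inputs from section 12.** SD 5 minutes, mean 30 minutes, planned difference 5 minutes, one-sided alpha 0.025, power 80%, 17 per group within each joint, 15% loss, 40 per joint (20 per arm).

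**The plan's own figure.** Normal approximation: n = 2 × (1.960 + 0.842)² × 5² / 5² = 15.7, so 16 per group. The noncentral t calculation gives power 78.1% at 16 and 80.7% at 17, so 17 is reproduced. With 15% loss, 34 / 0.85 = 40 per joint. The sample size is not in dispute.

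**Assumption.** The documents give no number of exclusions in theatre. I take k = 1, 2 or 3 of the 20 patients in one arm of one joint, with no true difference between techniques.

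**Bias.** If the k patients ranked highest by the surgeon's judgement leave the barbed arm only, and that judgement correlates ρ with closure time, then

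bias = -ρ × SD × (sum of the k largest expected normal order statistics for n = 20) / (20 - k).

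The three largest are 1.867, 1.408 and 1.131.

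| k lost, barbed arm only | ρ = 1 (exactly the slowest) | ρ = 0.5 |
|---|---|---|
| 1 | -5 × 1.867 / 19 = -0.49 min | -0.25 min |
| 2 | -5 × 3.275 / 18 = -0.91 min | -0.45 min |
| 3 | -5 × 4.406 / 17 = -1.30 min | -0.65 min |

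Against the planned 5 minutes, that is 10-26% in the worst case and 5-13% at ρ = 0.5.

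**One-sided error.** Simulation of the planned t-test at 0.025 (100,000 runs per scenario) confirms these biases and gives:

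| Patients lost | ρ = 1 | ρ = 0.5 |
|---|---|---|
| none | 2.6% | 2.5% |
| 1, barbed only | 5.5% | 3.6% |
| 2, barbed only | 9.3% | 4.8% |
| 3, barbed only | 14.0% | 5.9% |
| 2 barbed, 1 conventional | 6.2% | 3.6% |
| 1 from each arm | 3.5% | 2.7% |
| 1, conventional only | 1.4% | 1.8% |

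With one lost from each arm the bias is zero. The 3.5% at ρ = 1 arises because cutting the slowest closures also shrinks the observed SD. With two barbed and one conventional lost at ρ = 0.5, the bias is about -0.2 minutes.

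**Power.** Losses unrelated to arm or closure time cost precision only: power is 86.9% at 20 per arm and 80.7% at 17.

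**The case against.** The strongest reply is that the plan settles eligibility before allocation. Section 9.a has research personnel check every patient against the criteria before consent, section 3.2.2 randomises only those successfully screened, and no section re-applies the exclusions in theatre. Exclusions 3 and 7 mirror pre-operative indications, and some plastic-surgery closures are planned in advance. This largely stands for exclusions 3 and 7. It does not dispose of exclusion 8, which the operation itself can make true.

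A reader might infer that patients are randomised before the day of surgery and that the surgeon knows the arm throughout the operation. The documents say neither: the heading in 9.c is only pre-operative, the schedule in 9.f has no randomisation row, and a research assistant may draw the arm. What they do show is that nothing withholds it.

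A reader might also infer that exclusions will favour the barbed arm, or that exposure and incision length will shift with the arm. Nothing in the documents suggests a direction or a mechanism linking suture type to those decisions. Losses on the conventional side would reverse the bias, and balanced losses would remove it. The 14% figure needs exactly the three slowest closures to leave one arm, although a hand-over is decided before any closure time exists.

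Lost places are also largely covered. Closure time is measured in theatre, so the 15% margin for loss to follow-up can absorb losses there.

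Finally, a hand-over to plastics might be recorded as a closure deviation under section 5.1, and the unnamed analysis population is a more basic gap. Both are true, but naming a population would not recover a closure that did not happen.

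**Conclusion.** The concern holds as a weakness of design, not as evidence of bias. Allocation precedes surgery, the arm is not withheld until closure, and at least one exclusion can become true after allocation, so eligibility can depend on the arm.

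The size cannot be derived from the documents. Under the assumed one-arm losses of 1 to 3 in 20, a moderate link between judgement and closure time gives about -0.25 to -0.65 minutes and 4-6% error; -0.5 to -1.3 minutes and 5-14% is the extreme. Balanced losses leave essentially no bias. The same route could affect wound complications and scar ratings, but no figure can be given for those.

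The case for change rests on its low cost and on the small trial, where one or two patients per arm matter.

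**What to change.** Keep consent, screening and REDCap registration before surgery. Amend 3.2.2 and 9.c so that the arm is generated and revealed in theatre when the surgeon is ready to close, after:

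1. the surgeon has confirmed, and study staff have recorded, that exclusion 8 (and 3 and 7) does not apply; and
2. the incision length has been recorded.

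Patients found ineligible before that point are screen failures and are counted as such. Any patient lost after the reveal stays in the randomised set and is reported by arm with the reason.

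The cost is a protocol amendment, one REDCap step by study staff in theatre, and both suture sets available unopened. The randomised sample size is unchanged (17 per group, 40 per joint, 80 in total); a few more patients may need to be consented to replace screen failures. If allocation in theatre is not workable, reporting every post-randomisation exclusion by arm with its reason is a weaker substitute: it makes an imbalance visible but does not prevent it.

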**d. PERIOPERATIVE STUDY PROCEDURAL/DATA COLLECTION**

The following data points will be collected from the medical records and recorded in RedCap

1. Time of closure in seconds
2. Incision length
3. Number of sutures used
4. Any needle sticks or glove perforations
5. Type of dressing used (Aquacel or negative pressure dressing)

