#### *Secondary Objectives*

1. To evaluate the cost effectiveness of using bidirectional barbed suture compared with traditional sutures in revision knee and hip arthroplasty
2. To evaluate prevalence of complications (including needle sticks and glove perforations) of using barbed suture in revision total joint arthroplasty
3. To evaluate the cosmetic result of barbed versus traditional suture in revision total joint arthroplasty
4. To quantify the number of sutures used for each type of closure
5. To perform cost analysis to determine most cost-effective closure

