#### *Secondary Endpoints*

1. Record all complications (including needle sticks and glove perforations) and infections related to the wound closure
2. Calculate the cost difference based on supplies, personnel, and OR time between each technique
3. Gather pictures of wound following closure to evaluate the cosmetic result of barbed versus traditional suture in revision total joint arthroplasty using the Patient and Observer Scar Assessment Scale (POSAS)
4. Calculate the number of suture used and length of incision for each technique

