**e. FOLLOW-UP EVALUATION**  
**i. Post-operative hospital course**

All patients will be admitted to the hospital and discharge home or to a rehabilitation facility as deemed appropriate by the care management team. All patients will be weight bearing as tolerated unless otherwise dictated by the surgeon. Any wound complications or skin irritation documented will be documented in the subjects' medical records as part of standard of care.

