**Perioperative Variables**

Closure Time Incision Length Number of sutures used will be counted and recorded Any needle sticks or glove perforations Dressing Type Preoperative Incision Clinical Image
Postoperative Variables
Superficial wound complications: Skin irritation, erythema, suture spitting, cellulitis, superficial wound dehiscence, seroma, hematoma, prolonged wound drainage Deep wound complications: periprosthetic infection, arthrotomy failure, extensor mechanism failure Other non-closure associated complications Revision procedures for infection Revision procedures for any reason Post-operative antibiotic therapy Use of chronic antibiotic suppression therapy Post-operative Clinical Image (research only) POSAS Wound Score (research only)

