### Data Collection

After the patient has enrolled in this study, data will be directly collected from the patient and supplemented with electronic medical record (EMR) chart review. Additional data may be extracted from clinical notes. All members of the team will be trained in the reproducibly collection of clinical data. All data will then be input into REDcap. A member of the research team will be present at each patient follow-up to ensure that all necessary data points are collected. In addition, the research team may assist the physician when measuring the patient's functional outcomes.

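### Needle sticks and glove perforations are to be taken from the medical record, with nobody asked about them at closure, so a low or equal count could not be read as equal safety

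*Combined protocol and SAP*

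**What the plan says.** Section 2.2 (Secondary Objectives, item 2) sets the aim: "To evaluate prevalence of complications (including needle sticks and glove perforations) of using barbed suture in revision total joint arthroplasty". Section 2.3 (Secondary Endpoints, item 1) turns it into an endpoint, "Record all complications (including needle sticks and glove perforations) and infections related to the wound closure", without naming a source or a method.

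The source is given in section 9.d: "The following data points will be collected from the medical records and recorded in RedCap". Item 4 of the list beneath that sentence is "Any needle sticks or glove perforations".

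Section 11 (Data Collection) states generally that "data will be directly collected from the patient and supplemented with electronic medical record (EMR) chart review", and allows further data to be drawn from clinical notes. It places study staff at follow-up: "A member of the research team will be present at each patient follow-up to ensure that all necessary data points are collected". It says nothing of the operating room.

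The table of peri- and post-operative variables after the schedule of activities lists these events again. As far as its layout can be read, the instruction to count belongs to a different item: "Number of sutures used will be counted and recorded".

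**The concern.** A needle stick or a perforated glove happens to a member of the operating team. The patient cannot report it. The neighbouring section 9.e.i shows whose records the protocol has in mind when it says that wound complications "will be documented in the subjects' medical records as part of standard of care". No staff exposure log, occupational health record, end-of-closure question, glove inspection or event definition appears anywhere. Section 15 offers no second route, because the quarterly review described there is of subject safety data.

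Two problems follow. First, with no required yes/no entry, silence in the chart could mean that nothing happened or that nobody wrote it down. Second, the team knows which suture it is using, so voluntary noting could differ between arms.

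Section 1.2 gives fewer needles in staff hands as one reason for the trial, and section 1.1 cites glove perforation findings from primary arthroplasty. Readers will therefore look for this result in the revision setting. A low or equal count from an unqueried source could be taken as reassurance that the trial did not earn.

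**Working it through.** **1. What the plan provides for.** Setting the sections side by side:
- Sections 2.2 and 2.3: the events are to be evaluated and recorded; no method is given.
- Section 9.d: the source is the medical record.
- Section 11: the sources are the patient, the electronic record and clinical notes; staff presence is stated for follow-up visits.
- Variable table: the events are listed; counting is stated for sutures.
- Sections 9.e and 15: these concern the patient's complications and safety data.

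No section has anyone ask about or record these events at closure.

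**2. The plan's own figures.** Section 12 has no calculation for these events. Its only relevant figures are those for closure time, which set the number of closures. With a difference of 5 min, an SD of 5 min, one-sided alpha of 0.025 and 80% power, the normal approximation gives 16 per group. The t-test calculation gives 16.7, so 17, with power 80.7%. This agrees with the stated 17. Allowing for 15% loss, 34 / 0.85 = 40 per joint, or 80 in total. That is 40 per closure type if allocation is 1:1, which I assume.

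**3. Chance of no recorded event in either arm.** The documents give no event rate and no capture fraction, so both are assumed. With true rate p and capture fraction c in both arms, P(none in 80 closures) = (1 − pc)^80.
- p = 5%, c = 10%: 0.995^80 ≈ 67%
- p = 10%, c = 10%: 0.99^80 ≈ 45%
- p = 20%, c = 10%: 0.98^80 ≈ 20%
- p = 20%, c = 50%: 0.90^80 ≈ 0.02%

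**4. Effect on the comparison.** Section 12 specifies Fisher's exact test, two-sided at 0.05. The entries below are expected recorded events per arm (40 × p × c) and exact power at 40 vs 40, with the same capture in both arms.

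| True rates | Full capture | Half | Quarter | One tenth |
|---|---|---|---|---|
| 30% vs 10% | 12 vs 4; 53% | 6 vs 2; 18% | 3 vs 1; 3% | 1.2 vs 0.4; <0.1% |
| 20% vs 5% | 8 vs 2; 41% | 4 vs 1; 9% | 2 vs 0.5; 0.9% | 0.8 vs 0.2; <0.1% |
| 40% vs 10% | 16 vs 4; 85% | 8 vs 2; 41% | 4 vs 1; 9% | 1.6 vs 0.4; 0.3% |
| 10% vs 2% | 4 vs 0.8; 11% | 2 vs 0.4; 1% | 1 vs 0.2; <0.1% | 0.4 vs 0.08; <0.1% |

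Within one joint (20 vs 20), power with full capture is 24%, 17%, 49% and 3% for the four rows.

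**5. Unequal capture.** Suppose both arms have a true rate of 20%, and half the events are noted in one arm but a quarter in the other. The expected counts are 40 × 0.20 × 0.50 = 4 and 40 × 0.20 × 0.25 = 2, an apparent twofold difference where none exists.

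**The case against.** The sentence in section 9.d also governs closure time in seconds, incision length and suture count. The variable table says that sutures are counted, and the schedule puts the perioperative values on the day of surgery. The phrase about medical records may therefore mean that items are noted in theatre and then transcribed, not that someone later searches the chart for whatever it holds. Section 2.3 also shows an intention to record. The documents do not say what this hospital's perioperative record contains, so it is an inference that staff events are poorly captured there. Better capture would not rescue the comparison either: at several of the assumed rates power is low even when every event is recorded.

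Much of this stands. A reader might infer that the trial is bound to show few or no events whatever the truth. The documents do not support that. The capture rate is unknown, and step 3 shows that a complete absence of events is likely in one corner of the assumed grid and almost impossible in another.

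What does not stand is the suggestion that nothing need change. Closure time and suture count describe the patient's own operation; a staff injury does not, so sharing a sentence with them does not show that it will be charted. If recording in theatre is intended, the protocol should say so. Low power also makes the descriptive counts the main product, and they mean something only if every closure was asked about.

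**Conclusion.** The point holds as a defect in how a named secondary endpoint is ascertained. The stated source is ill suited to staff events, and no step at closure makes up for it. Under-recording is likely, but its size cannot be derived from the documents; all event rates and capture fractions above are assumptions, as is 1:1 allocation. If capture were incomplete the loss could be large: at 30% vs 10%, power falls from 53% to 18% at half capture and to 3% at a quarter.

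The conclusion that does not depend on those assumptions is narrower: a blank chart cannot be distinguished from no event, so a low or equal count could not be read as equal safety. The documents do not themselves plan such a claim. The primary endpoint's sample size is unaffected.

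**What to change.** In sections 9.d and 11, replace the medical record as the source for this item with a mandatory REDCap entry completed at skin closure. Staff already in the room put the same question to the team in both arms and enter:
- needle stick during closure: yes/no, and number;
- recognised glove perforation during closure: yes/no, and number.

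An explicit *no* must be entered, so that a missing answer is visible as missing. In section 2.3, call the endpoint *recognised* glove perforations, with a one-line definition of each event. Report the counts descriptively by arm, with the number of closures for which the item was completed.

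The cost is one short form item per operation and a few lines of protocol text; treatment and sample size do not change. The entry has to be in place before closures take place, since unrecorded events cannot be recovered from charts later. Some limits remain: reporting is still by an unmasked team, unnoticed perforations are still missed, and power is still limited.

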**e. FOLLOW-UP EVALUATION**  
**i. Post-operative hospital course**

All patients will be admitted to the hospital and discharge home or to a rehabilitation facility as deemed appropriate by the care management team. All patients will be weight bearing as tolerated unless otherwise dictated by the surgeon. Any wound complications or skin irritation documented will be documented in the subjects' medical records as part of standard of care.

